1.1.5.3. Exploratory Objectives

The exploratory objectives include the following:

- To describe the long-term efficacy of VGX-3100 with respect to combined histopathologic regression of anal or anal/peri-anal HSIL and virologic clearance of HPV-16 and/or HPV-18
- To describe the long-term efficacy of VGX-3100, as measured by histologic regression of anal or anal/peri-anal HSIL
- To describe the long-term efficacy of VGX-3100, as measured by virologic clearance of HPV-16 and/or HPV-18 by testing from lesion tissue
- To describe the long-term efficacy of VGX-3100, as measured by virologic clearance of HPV-16 and/or HPV-18 by intra-anal swab testing
- To evaluate tissue immune responses to VGX-3100 in intra-anal and/or peri-anal samples
- To describe the clearance of HPV-16 and/or HPV-18 infection from non-anal anatomic locations
- To describe the association of microRNA (miRNA) profile, previous anoscopy, cytology, and HPV testing results with Week 36 histologic regression
- To describe the patient reported outcomes (PRO) for subjects treated with VGX-3100
- To determine the humoral and cellular immune response following administration of VGX-3100 at post dose 3, and after additional dosing compared to baseline
- To determine the long-term efficacy of VGX-3100 with respect to histopathologic regression of anal or anal/peri-anal HSIL or virologic clearance of HPV-16 and/or HPV-18

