- The relationship of miRNA profile (baseline and at Weeks 15 and 36), previous anoscopy, cytology and HPV testing results with histologic regression of anal or anal/peri-anal HSIL at Week 36.
- Proportion of subjects with histologic regression or virologic clearance from intra-anal and/or peri-anal tissue at Week 64.

To assess quality of life and related impacts on subjects, PRO instruments will be administered and will include the SF-36v2TM, the EQ-5D-5L, and additional PRO questions assessing quality of life after surgery or biopsy.

- SF-36v2TM - generically measures functional health and well-being, for physical and mental health; consists of 36 items covering 8 domains (Physical functioning, Role limitations due to physical problems, Bodily pain, General health, Vitality, Social functioning, Role limitations due to emotional problems, and Mental health).
- EQ-5D-5L - generically measures activities & general health status; consists of 6 items covering 6 domains (Mobility, Selfcare, Usual activity, Pain/discomfort, Anxiety/depression, and Global health status)

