3.4. Baseline Definitions

For all analyses, baseline will be defined as the most recent measurement before the first administration of study drug.

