4.3.1. Primary Efficacy Endpoint

The primary endpoint is the combined response outcome of histologic regression of anal or anal/perianal HSIL and virologic clearance of HPV-16/18 in intra-anal and/or peri-anal lesion tissue at Week 36. Histologic regression is defined as no evidence of anal or anal/peri-anal HSIL on histology. Virologic clearance is defined as no evidence of HPV-16 and/or HPV-18 from intra-anal and/or peri-anal tissue by type-specific HPV testing. A treatment responder is defined as a subject with no histologic evidence of anal or anal/peri-anal HSIL and no evidence of HPV-16 or HPV-18 in anal lesion tissue and who did not receive any non-study treatment of curative intent of intra-anal and/or peri-anal lesions. A treatment non-responder is defined as a subject with histologic evidence of anal or anal/peri-anal HSIL, adenocarcinoma-in-situ, or anal or anal/peri-anal carcinoma, a subject with evidence of HPV-16/18 in anal lesion tissue, or a subject who received non-study treatment of curative intent of intra-anal and/or peri-anal lesions.

Table 2: Definition of Responder and Non-Responder for Primary Endpoint

Responder	Non-Responder

 • No histologic evidence of anal or anal/peri-anal HSIL in qualifying or new lesions AND • Negative PCR for HPV-16 or HPV-18 in anal lesion tissue in qualifying or new lesions AND • No non-study treatment of curative intent of intra-anal and/or peri-anal lesions 	
 • Histologic evidence of anal or anal/peri-anal HSIL, anal adenocarcinoma-in-situ, anal or anal/peri-anal carcinoma in qualifying or new lesions OR • PCR positive for HPV-16 or HPV-18 in anal lesion tissue in qualifying or new lesions OR • Any non-study treatment of curative intent of intra-anal and/or peri-anal lesions

Note: The efficacy time frame is defined by samples obtained any time starting from 14 days before the protocol-specified target date of Week 36. The first such sample determines the histology endpoint. The most recent HPV clearance result before time of the histologic and lesion sample within the time frame determines the HPV clearance endpoint.

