- Non-progression of anal or anal/peri-anal HSIL will be investigated at Week 36 for all subjects and separately at Week 64 for all subjects and also stratified by subjects who receive 3 or 4 doses. Progression is defined as advancement to carcinoma by histology according to the PAC.

Reduction in surface area of qualifying intra-anal and/or peri-anal lesion(s) at Weeks 36, 64, and 88 will be assessed and determined by quantitative analysis of standardized pre-biopsy digital photographic imaging. The mean percent change and associated 95% t-distribution based CI will be presented. A lesion will be considered qualifying if it is confirmed to be HPV-16 and/or HPV-18 positive and is histologically confirmed as intra-anal and/or peri-anal HSIL by the PAC at Screening.

The relationship between regression/clearance endpoints at Week 36 will be summarized with the number and percentage of subjects meeting the endpoint separately by previous HRA results, previous cytology results, and previous HPV test results. The relationship between the

regression/clearance endpoints at Week 36 with miRNA profiles will be summarized with the median change from baseline in miRNA profiles by those who achieved versus those who did not achieve the endpoint. A subject's miRNA profile is based on change from baseline normalized result to the latest normalized result obtained before the time of the Week 36 endpoint.

By-subject listings will be provided for all efficacy-related parameters and results.

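### The miRNA endpoint lists three time points, but section 4.3.2 plans one change score per subject, so baseline level and separate Week 15 and Week 36 results have no planned summary

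*SAP*

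**What the plan says.** The exploratory objective in SAP section 1.1.5.3 is descriptive: "To describe the association of microRNA (miRNA) profile, previous anoscopy, cytology, and HPV testing results with Week 36 histologic regression". Section 1.2.5.1 turns it into an endpoint and names the times: "The relationship of miRNA profile (baseline and at Weeks 15 and 36), previous anoscopy, cytology and HPV testing results", to be related to histologic regression at Week 36.

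The planned analysis is in section 4.3.2. The only miRNA summary there is the "median change from baseline in miRNA profiles by those who achieved versus those who did not achieve the endpoint". The same paragraph defines a subject's miRNA profile as "based on change from baseline normalized result to the latest normalized result obtained before the time of the Week 36 endpoint". By-subject listings of efficacy-related results are also planned.

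Two other definitions bear on this rule. Section 3.4 fixes the starting point: "baseline will be defined as the most recent measurement before the first administration of study drug". The note under Table 2 in section 4.3.1 fixes when the Week 36 histology endpoint occurs: "The efficacy time frame is defined by samples obtained any time starting from 14 days before the protocol-specified target date of Week 36", with the first such sample deciding the histology result.

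**The concern.** The endpoint lists three measurement times. The analysis returns one number per subject, and that number is a difference. Two things are lost.

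- **Baseline level.** It enters only by subtraction. No summary shows whether subjects who regressed had different miRNA levels before treatment.
- **Time after dosing.** Weeks 15 and 36 are alternatives within one score, not separate results. The rule that chooses between them turns on the word *before*, and the SAP does not say how that word applies to a sample taken on the day of the biopsy.

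At stake is whether the exploratory miRNA table can report what the endpoint names, and whether a reader can tell which week it describes. The study is open-label, so a time rule left open could be settled after outcomes are known.

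**Working it through.** **Plan's own figure.** The SAP gives no figure for the miRNA analysis. Its one design figure, about 80% power (section 3.1), reproduces with an exact one-sample binomial test. With 21 evaluable subjects, 15% against 40% and one-sided 0.05, rejection needs 7 or more responders; the attained alpha is 0.0287 and the power 0.7998. It has no bearing on this point. The rest is a comparison of texts plus simple arithmetic.

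**Step 1: endpoint against planned summary.**

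- Baseline: named in section 1.2.5.1; no summary of level by outcome in section 4.3.2.
- Week 15: named in section 1.2.5.1; no separate summary in section 4.3.2.
- Week 36: named in section 1.2.5.1; no separate summary in section 4.3.2.
- Change from baseline to one variable later time: the only summary by outcome in section 4.3.2.

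**Step 2: what a change score does to a baseline difference.** Let B be the baseline value and F the follow-up value, so the score is F − B. If achievers are higher by d at both times, the group difference in the score is d − d = 0, whatever d is.

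A simulation with assumed values, not SAP figures, shows the same for medians. It used 200,000 subjects, 40% of them achievers, baseline SD 1, and follow-up equal to baseline plus noise of SD 0.5.

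- d = 0.5 SD: median difference 0.51 in baseline level, −0.003 in change.
- d = 1.0 SD: median difference 1.00 in baseline level, −0.001 in change.

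A lasting baseline association of this kind would not appear in the planned table. This holds under any reading of the time rule.

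**Step 3: which later sample is used.** Three readings are open.

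- Same-day samples do not count as before: nearly all scores use Week 15, and Week 36 largely drops out.
- Same-day samples count: most scores use Week 36, and Week 15 is a fallback when the Week 36 sample is missing.
- The rule follows actual order within the visit, or sampling and biopsy fall on different days: some subjects contribute Week 15 and others Week 36.

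The histology sample can also come up to 14 days before the Week 36 target date. A biopsy early in that window could precede the Week 36 miRNA sample and move that subject to Week 15. No reading gives separate results for both weeks.

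**Step 4: how far apart the candidates are.** Dose 3 is at Week 12 (section 1.2.1).

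- Between the samples: 36 − 15 = 21 weeks.
- After dose 3: 15 − 12 = 3 weeks against 36 − 12 = 24 weeks.

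**Step 5: group size.** At the planning rate in section 3.1, 0.40 × 24 = 9.6 achievers. With 90% evaluable, 24 × 0.90 = 21.6 and 0.40 × 21.6 = 8.6. The 40% is for the combined primary endpoint; histologic regression alone is at least as frequent. The groups are small, but the SAP gives no miRNA variance, so the shift in a median from any mixing cannot be calculated.

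**The case against.** The strongest reply is that the objective only asks for a description, and a median change by outcome plus by-subject listings does describe part of the association. The rule also has a rationale: it uses no sample taken after the outcome, and it keeps subjects who missed a visit. The table shells are separate documents, so extra by-visit displays cannot be ruled out.

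Much of this stands, and it limits the point. Several stronger readings are tempting but not supported:

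- *The endpoint cannot be answered.* The change component is answered, and individual values may be listed. Only the baseline-level and visit-specific parts lack a planned summary.
- *The analysis mixes Weeks 15 and 36.* Mixing is possible, not certain. If the rule is applied by date, same-day samples count for everyone or for no one, and mixing then comes only from missing samples or split visit days.
- *The order of blood draw and biopsy decides the time point.* The SAP does not name the miRNA specimen, so a blood draw is an assumption.
- *Baseline miRNA is the only pre-treatment factor considered.* Previous anoscopy, cytology and HPV results are in the same endpoint, and section 4.3.2 summarises outcome by each.

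What the reply does not meet is the mismatch itself. Listings do not replace a pre-specified summary, and the SAP text, followed exactly, gives one score where its endpoint names three times.

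**Conclusion.** The point holds as a mismatch between a stated endpoint and its stated analysis. Section 1.2.5.1 lists baseline, Week 15 and Week 36; section 4.3.2 plans a single change score. The absence of a baseline-level comparison and of separate Week 15 and Week 36 results follows from the text alone and needs no assumption about visit order or specimen. The same-day rule is undefined. Its consequence ranges from mostly Week 36 to mostly Week 15, with some mixing possible in between.

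The impact is low. The endpoint is exploratory, formal testing is confined to the primary endpoint (section 3.2), and the primary result is unaffected. The simulated differences in baseline level are illustrations under assumed values and say nothing about how large any real miRNA association is.

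**What to change.** In section 4.3.2, replace the single score with three descriptive summaries by Week 36 outcome:

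1. baseline normalized level;
2. change from baseline to Week 15;
3. change from baseline to Week 36.

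Use nominal-visit samples for each, and state that the Week 36 sample is eligible when taken on the day of the biopsy. Describe all three as associations. A single-arm study cannot separate prediction of treatment effect from prognosis, so the word *predictive* should be avoided. Label the Week 36 summary as concurrent with the outcome. Section 4.3.4 already analyses ELISpot and ELISA at each visit, so this follows the SAP's own convention.

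The cost is a change of wording and two more tables, from time points that the endpoint already lists. Each row may hold slightly fewer subjects when a sample is missing, because the fallback to another visit is gone.

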4.3.3. Patient-Reported Outcomes

PRO assessments will be performed at Day 0 before first dose, on the day of and after each dose, and at Weeks 36, 64, and 88. There will be an additional PRO assessment at Week 40 if a subject receives a fourth dose.

For the SF-36v2 results, scores and changes from baseline for the 8 subscales (Physical Functioning, Role Physical, Bodily Pain, General Health, Vitality, Social Functioning, Role Emotional, and Mental Health) as well as the Physical Component Summary (PCS) and Mental Component Summary (MCS) will be summarized using medians and associated exact non-parametric 95% CIs.

For the EQ-5D-5L results, the scores for 5 health categories (1-5 scales) and overall health score (1-100 scale) will be summarized; the scores and changes from baseline will be summarized using medians and associated exact non-parametric 95% CIs.

For the 2 additional global PRO questions assessing quality of life after surgery or biopsy, the time outcome will be summarized with a median and associated exact non-parametric 95% CI, and the binary yes/no outcomes will be summarized with a proportion and associated exact Clopper-Pearson 95% CI.

All PRO data will be presented by study visit in data listings.

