3. GENERAL STATISTICAL METHODS

3.1. Sample Size Justification

The trial will enroll 24 subjects. This sample size provides ~80% power to declare superiority over historical control, assuming the true proportion of subjects who achieve the primary endpoint is 40% for the treatment arm versus 15% for the historical control, and that 90% are evaluable at Week 36 from first dose.

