3.2. General Methods

All data listings that contain an evaluation date will contain a relative study day (Rel Day). Pre-treatment and on-treatment study days are numbered relative to the day of the first dose of study medication which is designated as Day 1. The preceding day is Day -1, the day before that is Day -2, etc. There is no Rel Day 0.

All output will be incorporated into Microsoft Word or Excel files, or Adobe Acrobat PDF files, sorted and labeled according to the International Council for Harmonisation (ICH) recommendations, and formatted to the appropriate page size(s).

Tabulations will be produced for appropriate demographic, baseline, efficacy, immunogenicity, and safety parameters. For categorical variables, summary tabulations of the number and percentage of subjects within each category (with a category for missing data) of the parameter will be presented. For continuous variables, the number of subjects, mean, median, standard deviation (SD), minimum, and maximum values will be presented. Summarizations will be presented by overall as applicable.

Formal statistical hypothesis testing will be performed on the primary endpoint compared with historical control at the 1-sided, 0.05 level of significance. Summary statistics will be presented, as well as 2-sided confidence intervals (CIs) on selected parameters, as described in the sections below.

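### SAP 4.3.3: a median with an exact CI tells little about change on the five-level EQ-5D-5L items; at 24 subjects it reads 0 (0 to 0) with up to 6 worse and the rest unchanged

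*SAP*

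**What the plan says.** Section 4.3.3 sets the EQ-5D-5L analysis. It first names the data: "the scores for 5 health categories (1-5 scales) and overall health score (1-100 scale) will be summarized". It then gives one method for all of them: "the scores and changes from baseline will be summarized using medians and associated exact non-parametric 95% CIs". The SF-36v2 subscales and component summaries get the same treatment. The yes/no global questions in that section get a proportion with a Clopper-Pearson interval. For the five items, the section names no shift table and no proportion improved or worsened. All PRO data are also to be listed by visit.

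Section 3.2 sets defaults for all tabulations: "For categorical variables, summary tabulations of the number and percentage of subjects within each category", and for continuous variables n, mean, median, SD, minimum and maximum. It adds two-sided intervals for selected parameters as later sections describe. It confines formal testing to the primary endpoint.

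Section 1.1.5.3 lists the PRO objective as exploratory and descriptive.

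**The concern.** A change on a five-level item is a small integer, and in a short series many subjects may not move at all. The median then sits on the tied value, and so can both order statistics that form its exact interval. The table can read 0 (0 to 0) while a minority of subjects is worse, or while some are worse and others better. The objective is to describe how subjects fare, and PROs are collected around each dose as well as at later visits. A row that looks the same with 0 or with 6 of 24 subjects worse describes little.

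**Working it through.** **Inputs.**
- Sample size, Section 3.1: "The trial will enroll 24 subjects".
- Evaluable share, Section 3.1: "and that 90% are evaluable at Week 36 from first dose". 24 × 0.9 = 21.6, so 21 or 22. This share is stated for Week 36; using it for the PRO data is an assumption.
- Five items on 1-5 scales, median and exact two-sided 95% CI: Section 4.3.3.
- Assumptions that are not in the SAP: a higher level is worse (the argument is symmetric if it is not), and every subject who has not worsened is unchanged. The SAP gives no expected EQ-5D-5L distribution.

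**The plan's own figure.** The SAP states no figure for the EQ-5D-5L. Its only figure is the power for the primary endpoint ("This sample size provides ~80% power to declare superiority over historical control", 40% against 15%, one-sided 0.05). It reproduces with an exact binomial test: n = 24 needs at least 8 responders (alpha 0.0199, power 80.8%); n = 21 needs at least 7 (alpha 0.0287, power 80.0%); n = 22 needs at least 7 (alpha 0.0368, power 84.2%). So 24, 22 and 21 are sensible sizes to work with here.

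**Step 1: ranks of the exact interval.** The interval for a median runs from X(l) to X(n+1−l), where l is the largest rank with P(Bin(n, 0.5) ≤ l−1) ≤ 0.025. For n = 24, P(≤ 6) = 0.0113. Adding C(24,7)/2^24 = 346,104/16,777,216 = 0.0206 gives 0.0320, which is too large. So l = 7 and the interval is X(7) to X(18), with coverage 1 − 2 × 0.0113 = 97.7%.

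**Step 2: how many can worsen before the output changes.** With w subjects worse and n − w at 0, the upper limit stays 0 while n − w is at least n + 1 − l, that is, while w ≤ l − 1.

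| n | Interval | Coverage | Largest w giving 0 (0 to 0) | Upper limit leaves 0 at | Median leaves 0 at |
|---|---|---|---|---|---|
| 24 | X(7) to X(18) | 97.7% | 6 (25.0%) | 7 | 12 |
| 22 | X(6) to X(17) | 98.3% | 5 (22.7%) | 6 | 11 |
| 21 | X(6) to X(16) | 97.3% | 5 (23.8%) | 6 | 11 |

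At n = 24, six worse and six improved also gives 0 (0 to 0): the ordered changes are 6 negative, 12 zero and 6 positive, so the 7th and 18th values are both 0.

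**Step 3: how often this would happen.** If a true share p worsens and nobody improves, P(0 to 0) = P(Bin(n, p) ≤ l − 1).

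| p | n = 24 | n = 22 |
|---|---|---|
| 0.20 | 0.81 | 0.73 |
| 0.25 | 0.61 | 0.52 |
| 0.30 | 0.39 | 0.31 |
| 0.40 | 0.10 | 0.07 |

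**Step 4: the same data in other summaries.** Take 6 of 24 worse by one level and 18 unchanged.
- Planned: median 0, CI 0 to 0.
- Proportion worse: 6/24 = 25%. Clopper-Pearson limits are the 0.025 quantile of Beta(6, 19) and the 0.975 quantile of Beta(7, 18), giving 9.8% to 46.7%.
- Mean change: 6/24 = 0.25, SD 0.442, standard error 0.442/√24 = 0.090, t-based 95% CI 0.06 to 0.44.

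**The case against.** The strongest reply is that the median is not the whole output. Section 3.2 covers efficacy parameters, Section 4.3.3 sits under the efficacy evaluation, and the section-level intervals can be read as additions to the default summaries. Either default would show a shift: level percentages would move, and in the example above the mean change is 0.25. This stands, so it would be wrong to say that the items are summarised by the median alone. What it leaves open is which default applies. Section 4.3.3 treats the items as scores, which points to the continuous rule, while five levels point to the categorical one. Level percentages at each visit would also not show how many individual subjects moved. The table shells (Section 7.2) are a separate document and may settle this, but the SAP text does not.

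Three stronger readings are tempting, and the document does not support them.
- *That the analysis cannot detect change.* No PRO test is planned and the objective is descriptive. The upper limit moves at 7 of 24, and at a true 25% worsening the interval is wider than 0 to 0 with probability 1 − 0.61 = 0.39.
- *That the zero-width interval is false precision.* It is a valid interval for the median with at least 95% coverage. If most changes are 0, the median change is 0. It misleads only a reader who takes it to mean that nobody changed.
- *That tolerability information is lost.* Post-dose local and systemic events come from diary cards (Section 1.2.5.3). Section 4.4.2 includes injection site reactions in the adverse event summaries and gives preferred-term frequencies within 7 and 28 days of dosing with exact Clopper-Pearson intervals. The SF-36v2 Bodily Pain and Mental Health subscales are summarised too.

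**Conclusion.** The point holds as a matter of a poorly suited descriptive summary. On the five items, the median and exact CI read 0 (0 to 0) with up to 6 of 24 worse, or up to 5 of 21 or 22, if the rest are unchanged. A quarter is therefore the boundary at full enrolment, and the share is slightly lower at the planned evaluable numbers. The SAP does not fix which default summary accompanies the median, and it plans no count of subjects who improved or worsened.

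The size depends on how many changes are tied at 0, which the SAP does not forecast; the shares worsening used above are illustrations. The argument does not carry over in the same way to the overall health score, which has a much finer scale. The endpoint is exploratory and no primary or secondary conclusion depends on it, so this is a low-priority improvement.

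**What to change.** In Section 4.3.3, separate the five EQ-5D-5L items from the overall health score. For each item and visit, report n (%) at each level, and n (%) improved, unchanged and worsened by at least one level from baseline, with Clopper-Pearson 95% CIs, using as denominator the subjects with both values. The section already uses that interval for the yes/no questions. Keep the median and exact CI for the overall health score and the SF-36v2 scales.

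The cost is a short wording change and one revised table, with no new data. The downside is a few more rows per visit.
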